### **Composite Angiotensin Receptor-Nepriylsin Inhibition may reduce Central Aortic Stiffness in Heart Failure and Improve Ventricular-Vascular Coupling**

Traditional afterload reduction with peripheral vasodilator drugs reduces peripheral resistance, MAP and wave reflection, but does not reduce  $Z_c$ . If cardiac output increases because of the reduction in peripheral resistance, pulsatile overhead will paradoxically increase because the additional flow must be transferred through  $Z_c$ , which remains high. In addition, even more pulsatile energy will be transmitted to the periphery because of the reduction in wave reflection. Thus, traditional vasodilator drugs reduce MAP, which is often already either normal or low in patients with heart failure, yet increase pulsatile stress on the LV and arterial system.

Angiotensin-converting enzyme (ACE) inhibitors and angiotensin-receptor blockers (ARB) may reduce aortic stiffness by opposing vasoconstrictive, hypertrophic, and profibrotic effects of angiotensin II on the vessel wall. Nepriylsin or neutral endopeptidase (NEP) is an enzyme that inactivates several vasodilatory peptides including the natriuretic peptides that are thought to play a role in the body's defense against hypertension. Data from experimental models suggests that natriuretic peptides may have favorable effects on the aorta. Combined

ACE/NEP inhibition with omapatrilat 80 mg was associated with greater reductions in pulse pressure and  $Z_c$  than enalapril 40 mg in the Conduit Hemodynamics of Omapatrilat International Research Study (CHOIR), but was associated with an unacceptable risk of

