#### **3.6.1 Risks**

Experience in the PARADIGM-HF trial, both in the run-in period as well as the double-blind randomization period, indicated that the major risks associated with the treatment of sacubitril/valsartan are renal dysfunction, [426 (10.14%) in 4203 patients in the double-blind treatment period], hyperkalemia, [488 (11.61%) in 4203 patients in the double-blind treatment period], and hypotension [740 (17.61%) in 4203 patients in the double-blind treatment period].

In PARADIGM-HF, patients treated with enalapril experienced these events at a similar rate with the exception of hypotension; renal dysfunction, [487 (11.52%) in 4229 patients in the double-blind treatment period]; hyperkalemia, [592 (14%) in 4229 patients in the double-blind treatment period]; and hypotension, [506 (11.97%) in 4229 patients in the double-blind treatment period]. Results from the TITRATION study indicated that patients whom are ACE or ARB naïve are at an increased risk of experiencing these adverse events.

In this study, the risk of experiencing renal dysfunction, hyperkalemia, and hypotension are mitigated by appropriate up-titration of the drug every two weeks. The risks are further mitigated by appropriate inclusion and exclusion criteria. Patients entering into the study must have an SBP of at least 140 mmHg if not treated for hypertension or a SBP of >105 mmHg if

they are currently on treatment. Additionally, patients are excluded if they have an eGFR < 30 ml/min/1.73 m^2 or a potassium > 5.2 mEq/L at screening.

Drug to drug interactions are known to occur with concomitant use of ACE/ARB/NEP and renin inhibitors. See [Section 5.5.8](#) for prohibited medications. Patient will be provided with study treatment instructions and their medication histories will be reviewed at Screening and all subsequent visits.

Sacubitril/valsartan, [19 (0.5%) in 4203 patients in the double-blind treatment period of PARADIGM-HF] and enalapril 10 (0.2%) in 4229 patients in the double-blind treatment period of PARADIGM-HF] may also cause angioedema. The risk of developing angioedema is increased if patients take both an ACEi and sacubitril/valsartan. To decrease this risk, patients will be required to undergo a 36-hour washout prior to randomization as well as the open-label treatment epoch to minimize the interaction between an ACEi and sacubitril/valsartan in potentiating the development of angioedema.

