In the PARADIGM-HF study, sacubitril/valsartan reduced the risk of CV death and HF hospitalization versus enalapril. In the US, sacubitril/valsartan is approved and indicated to reduce these risks in patients with chronic heart failure (NYHA class II-IV) and reduced ejection fraction. Due to this, the double-blind treatment epoch is limited to 12 weeks to minimize the chance of exposure to standard treatment with enalapril. Thereafter, all patients will have the opportunity to receive 12 weeks of open-label sacubitril/valsartan. It should be noted that the population of patients studied in PARADIGM-HF included NYHA class II-IV patients that were all on either ACEi or ARBs prior to study enrollment. The population of patients included in this study is different than that of PARADIGM-HF.

There is a chance a patient may develop signs and symptoms of worsening heart failure for which the investigator would like to administer appropriate therapy. Appropriate adjustments, intensifications, or additions to concomitant medications should be considered. If needed, the investigator can choose to withdraw the patient from the study to initiate treatment with sacubitril/valsartan, ACEi, or ARBs if the investigator believes this to be appropriate treatment. Rescue options are provided in [Section 5.5.6](#).

In addition to investigational treatment, all patients will be allowed to continue receiving the rest of their background cardiovascular (CV) medications throughout the study. Patients will be randomized to study treatment only after the investigator has confirmed the patient is on stable treatment with guideline-directed therapy for HFrEF, other than ACEis and ARBs, which will ensure that patients are receiving appropriate treatment for their heart failure.

The study procedures and assessments for this study are either non-invasive or minimally invasive (venipuncture for blood draws) and are considered low risk.

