A qualified echocardiographer and a trained site professional will obtain the following hemodynamic measurements using arterial tonometry with electrocardiogram, using a custom transducer from the Cardiovascular Engineering, Inc. core lab.

1. brachial, radial, femoral and carotid pulsatile pressures
2. body surface measurements from suprasternal notch to pulse recording sites, using a fiberglass tape measure for carotid, brachial and radial sites and a caliper for the femoral site.

All blood pressure acquisitions and tonometry waveforms will be transmitted to the Hemodynamic Core Lab at Cardiovascular Engineering, Inc. for overreads. Tonometry waveforms will be signal-averaged using the electrocardiogram R-wave as a fiducial point. Carotid-femoral pulse wave velocity (CFPWV) will be calculated from ECG-gated carotid and femoral arterial waveforms and body surface measurements. Doppler audio signals recorded in the left ventricular outflow tract will be analyzed and signal averaged using custom software. The resulting high resolution flow waveform will be extracted and paired with the calibrated pressure waveform in order to perform central pressure-flow analysis. Characteristic impedance will be computed as the ratio of change in pressure divided by change in flow as assessed from the foot of the respective waveforms to the time when flow reaches 95% of peak flow. Joint analysis of pressure and flow waveforms will be used to separate forward, reflected waves, and measure their amplitudes. Augmentation index will be assessed from the carotid pressure waveform.

Carotid artery flows will be analyzed from digitized Doppler audio data using a semi-automated signal-averaging approach as detailed previously by (Mitchell, et al. 2004, 2011). Flow spectra are signal-averaged (1000 Hz resolution) using the electrocardiogram as a fiducial point. Flow velocities are multiplied by carotid artery cross-sectional area to obtain volume flows. Carotid volume flows will be paired with the carotid pressure waveform to perform carotid artery pressure-flow analysis and to model transmission of pulsatility into the carotid circulation (Mitchell 2011). Carotid pulsatility index will be computed for each carotid by dividing the flow pulse amplitude (peak flow minus flow at the onset of the systolic upstroke) by mean flow. Values for the right and left carotid will be averaged.

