2.2.1 Subgroup of interest

The following subgroups will be analyzed for the primary objective:

1. Age groups (<65, ≥65 years; and <75, ≥75 years)
2. Baseline ejection fraction categories based on echocardiography (<25%, 25% - <35%, ≥35%)
3. Prior ACEi/ARB exposure groups (never exposed, previously exposed, or currently taking)
4. Prior ACEi/ARB dose groups (low dose, high dose) (e.g., low dose: <10 mg enalapril daily [or equivalent]; high dose: ≥10 mg enalapril daily [or equivalent])

5. Baseline quartiles of aortic characteristic impedance (based on FAS)
6. Baseline estimated glomerular filtration rate (eGFR) categories (<45, 45 - <60, ≥60 ml/min/1.73 m²)
7. Groups defined by quintiles of change from baseline in mean arterial pressure at Week 12 (based on FAS)
8. New York Heart Association (NYHA) classification [best value during the past month prior to screening visit] (I, II, III, IV)
9. Prior heart failure hospitalization (No, Yes)
10. Prior diabetes (No, Yes)
11. Baseline plasma NT-proBNP (pg/mL) categories (≤ median, > median) (based on FAS)

See Section 2.5 for further details on the primary objective.

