2.5.2 Statistical hypothesis, model, and method of analysis

Let μ_j denote the population mean of change from baseline in the aortic characteristic impedance at Week 12 for treatment group j , $j = 0, 1$, where 0 corresponds to enalapril and 1 corresponds to sacubitril/valsartan.

The following null hypothesis (H_0) will be tested against the alternative hypothesis (H_A):

$$H_0: \mu_1 - \mu_0 = 0$$

$$H_A: \mu_1 - \mu_0 \neq 0$$

The primary endpoint will be analyzed by an analysis of covariance (ANCOVA) model with treatment and Z_c baseline as explanatory variables (Mitchell 2002). The least squares means of the two treatment groups, least squares mean difference of the treatment groups, 95% confidence interval for the difference in the two treatment groups, and p-value based on the fitted linear model will be reported. If the p-value is < 0.05 and the least squares mean difference

of the treatment groups favors sacubitril/valsartan, statistical significance in favor of sacubitril/valsartan is shown.

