2.5.4 Supportive analyses

A supportive nonparametric analysis will be performed to examine the consistency of results if the assumption of normality for the distribution of the primary endpoint is not tenable. Graphical methods (e.g., normal probability plot and histogram of residuals) and analytical methods (e.g., Shapiro-Wilk test) will be used to assess the assumption of normality. For this supportive analysis, the primary endpoint will be analyzed using the Wilcoxon rank-sum test. The probability of one treatment being the same or better than the other treatment will be estimated (based on the Wilcoxon rank-sum test) and the associated 95% confidence interval will be reported (Chen and Kianifard, 2000).

The following supportive/sensitivity analyses of the primary endpoint will also be performed:

- An analysis based on the FAS using the same analytical approach as described in Section 2.5.2 where missing values at Week 12 are imputed using the Last Observation Carried Forward (LOCF) procedure (only post-baseline trough values will be carried forward).
- An analysis based on the PPS using the same analytical approach as described in Sections 2.5.2 and 2.5.3.
- Change from baseline in aortic characteristic impedance at Weeks 4 and 12 will be analyzed based on a repeated measures ANCOVA model in which treatment, week, and treatment-by-week interaction will be included as fixed-effect factors and the baseline value as a covariate, with a common unstructured covariance for each treatment group. The primary treatment comparison between sacubitril/valsartan and enalapril will be made at Week 12. The analysis will be performed on all available data in the FAS. The estimated treatment effect with the associated two-sided 95% confidence interval at Week 12 will be provided.
- Subgroup analyses based on the FAS as described in Section 2.2.1.
- An on-treatment analysis based on the FAS using the using the same analytical approach as described in Section 2.5.2.
- Analyses of the “original” and “alternative” aortic characteristic impedance variables based on the FAS using the same analytical approach as described in Section 2.5.2.

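### SAP 2.2.1 lists Week 12 change in mean arterial pressure as a subgroup factor; it is measured after randomisation, so the Zc differences within its quintiles are not randomised comparisons

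*SAP*

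**What the plan says.** SAP 2.2.1 (Subgroup of interest) names the factors by which the primary objective will be examined. Ten of the eleven describe the patient before treatment: age, baseline ejection fraction, prior ACEi/ARB exposure and dose, baseline Zc, baseline eGFR, NYHA class before screening, prior heart failure hospitalisation, diabetes, and baseline NT-proBNP. Item 7 is the exception: "Groups defined by quintiles of change from baseline in mean arterial pressure at Week 12 (based on FAS").

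SAP 2.5.4 (Supportive analyses) puts all eleven in one bullet: "Subgroup analyses based on the FAS as described in Section 2.2.1". Neither section, nor the list of changes in SAP section 4, gives item 7 a separate method, estimand or warning in the text available. Parts of the SAP are redacted, so this describes what can be read.

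The primary analysis in SAP 2.5.2 is separate: "The primary endpoint will be analyzed by an analysis of covariance (ANCOVA) model with treatment and" baseline Zc as explanatory variables.

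**The concern.** A subgroup analysis of a randomised trial is protected by randomisation because the groups exist before treatment starts. A quintile of on-treatment MAP change may itself be a result of treatment. Two links decide whether that matters.

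1. **Treatment may move MAP.** Protocol 3.6.1 reports, from PARADIGM-HF, "and hypotension [740 (17.61%) in 4203 patients in the double-blind treatment period" on sacubitril/valsartan, "and hypotension, [506 (11.97%) in 4229 patients in the double-blind treatment period" on enalapril. The same section warns: "The population of patients included in this study is different than that of PARADIGM-HF".
2. **MAP change and Zc change may share causes or error.** Under Protocol 6.4.1, Zc comes from a flow waveform "paired with the calibrated pressure waveform in order to perform central pressure-flow analysis", so an error in pressure at Week 12 could enter both changes.

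If both links hold, patients in the two arms with the same MAP change differ systematically in other respects that bear on Zc. If instead MAP change causes Zc change, each row holds constant something through which the drug works, and that part of the effect disappears from the row. In neither case does a row show the primary treatment effect in a kind of patient, which is what the other ten items show.

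The question behind item 7 is reasonable. Protocol 1.1 argues that conventional vasodilator therapy "reduces peripheral resistance, MAP and wave reflection, but does not reduce" Zc, so readers of a mechanistic trial will want to know whether a Zc effect is independent of pressure. That makes these rows likely to be read as evidence on the matter, and as planned they would appear among ordinary subgroups.

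**Working it through.** **Plan's own figure.** Inputs from Protocol 9.8 and SAP section 3: difference 30, SD 80, 90% power, 20% dropout, 10% non-evaluable; two-sided 0.05 from SAP 2.1.

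- Per arm: 2 × (1.960 + 1.282)² × 80² / 30² = 149.4, so 150 (151 with the t distribution).
- Losses added to 30%: 151 / 0.70 = 215.7, so 216 per arm and 432 in total. The plan's number is reproduced.
- Losses applied in sequence (0.8 × 0.9 = 0.72): 150 / 0.72 gives 209 per arm, 418 in total.

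**Precision of one row.**

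- Evaluable patients: 432 × 0.72 = 311, or 432 × 0.70 = 302.
- Per arm per quintile: 31.1 or 30.2.
- 95% half-width: 1.96 × 80 × √(2/31.1) = 39.8, or 1.96 × 80 × √(2/30.24) = 40.3.

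**Assumed quantities.** The documents give no treatment effect on MAP and no MAP–Zc correlation. I take an arm difference in MAP change of d = 0.2 to 0.4 SD (lower on sacubitril/valsartan) and a correlation r of -0.3 to 0.5. The only anchor in the documents is indirect. On a probit scale, 740/4203 and 506/4229 correspond to -0.930 and -1.177, a shift of 0.246 SD. Reading hypotension rates as a shift in MAP change is itself an assumption.

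**Model.** Let T = 1 for sacubitril/valsartan, and U and E be independent standard normals. MAP change in SD units is M = -dT + U. Quintiles of M are taken over both arms pooled. Differences are sacubitril/valsartan minus enalapril, in dyne x sec/cm5, from 2,000,000 simulated patients per setting.

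*A. Shared causes or error, true Zc effect zero:* Zc change = 80(rU + √(1-r²)E). At an exact value of M, U is larger by d on sacubitril/valsartan, so the arm difference is 80rd. Quintiles are coarser than exact matching, so the bias is slightly smaller. Average over the five rows:

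| d | r = -0.3 | r = 0 | r = 0.3 | r = 0.5 |
|---|---|---|---|---|
| 0.2 | -4.4 | 0.0 | 4.3 | 7.1 |
| 0.25 | -5.3 | -0.1 | 5.1 | 8.9 |
| 0.4 | -8.7 | 0.0 | 8.7 | 14.4 |

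For example, 80 × 0.5 × 0.25 = 10.0 under exact matching, against 8.9 by quintile. The most extreme single rows are -9.5 and +15.8. The overall randomised difference stays at zero throughout.

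*B. MAP change drives Zc change, no direct effect:* Zc change = 80(rM + √(1-r²)E). The true overall difference is -80rd. Overall difference against five-row average:

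| d | r = -0.3 | r = 0.3 | r = 0.5 |
|---|---|---|---|
| 0.2 | 4.7 vs 0.4 | -4.8 vs -0.5 | -7.9 vs -0.8 |
| 0.25 | 6.0 vs 0.6 | -5.9 vs -0.5 | -10.0 vs -1.0 |
| 0.4 | 9.7 vs 1.2 | -9.7 vs -1.1 | -16.0 vs -1.6 |

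In both cases the sacubitril/valsartan share of the lowest quintile is 57%, 59% and 64% at d = 0.2, 0.25 and 0.4, where randomisation would give 50%.

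*With a real effect of -30 and shared causes, d = 0.3:* the rows run from about -18 to -21 at r = 0.5, and from about -35 to -37 at r = -0.3.

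**The case against.** The strongest reply concerns weight. Item 7 is one of eleven supportive subgroup sets, and no alpha, success rule or decision attaches to it. At the one shift tied to a document figure, the assumed bias (-5.3 to +8.9) is small beside a row interval of ±40, so the rows would support little inference even without bias. That stands and limits the importance of the point. It does not make the rows interpretable, and a consistent pattern over five rows can persuade even when each row is imprecise.

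The magnitudes are assumed, and hypotension rates over the whole double-blind period of another trial, in a different population, are a weak guide to mean MAP change at 12 weeks here. This also stands: the figures illustrate and do not measure. If treatment does not shift MAP, or MAP change and Zc change are unrelated, the bias is zero. The average over five rows is a summary used here; the SAP does not plan it.

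Case B can be read differently. If MAP change drives Zc change, rows near zero correctly answer whether the effect is independent of pressure. That is fair, but it is a mediation question with its own assumptions, and a subgroup table invites another reading.

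SAP 2.5.4 does not spell out the within-quintile model, and the table shells and redacted sections cannot be seen. Arm differences within quintiles are the natural reading of its bullet, though not stated text.

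**Conclusion.** The point holds. Item 7 is the only listed subgroup factor measured after randomisation, and the readable text treats it as an ordinary subgroup. Its within-quintile Zc differences are open to bias of unknown size and sign.

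Under the assumptions shown, shared causes would move the average row by -8.7 to +14.4 across the range examined, against a planned difference of 30. If MAP change is the pathway, the rows would show -1.6 to +1.2 where the overall effect is -16.0 to +9.7. The unprotected status of the comparison follows from the definition of the groups. The sizes rest on the assumed shift, correlation and causal structure.

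The consequence is confined to this supportive analysis. The primary ANCOVA, its p-value, the success rule and the sample size do not change. It should be corrected because it is cheap to correct and bears on a mechanistic claim that readers are likely to draw.

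**What to change.** Delete item 7 from the list in SAP 2.2.1. If pressure-independence of the Zc effect is of interest, add a separate bullet to SAP 2.5.4, for example:

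> Exploratory, non-randomised (mediation-type) analysis: the ANCOVA of Section 2.5.2 with Week 12 change in mean arterial pressure added as a covariate, and Zc change by quintile of that change shown descriptively. The adjusted difference can be read as a direct effect only if no unmeasured factor affects both changes and their relation is the same in both arms. It is not presented with the subgroup results.

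The added model does not remove the bias of case A; conditioning on MAP change leaves it at about 80rd. What it provides is a stated question, stated assumptions and separation from the randomised subgroups. If a blood-pressure subgroup is also wanted, use quintiles of baseline MAP. That asks whether the effect varies with starting pressure and does not replace the exploratory analysis.

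Cost: one list item removed, one bullet added, one extra model and table, no new data. The drawback is that MAP-change rows no longer appear among the subgroup results, and the exploratory estimate rests on assumptions the trial cannot check.

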2.3 Patient disposition, demographics and other baseline characteristics

2.3.1 Patient disposition

All patients will be used for the summary of patient disposition. The following categories will be summarized:

- Number of patients who were screened
- Screening phase disposition
 - Completed
 - Adverse event
 - Death
 - Pregnancy
 - Screen failure
 - Study terminated by sponsor
 - Technical problems
 - Lost to follow-up
 - Physician decision
 - Subject/Guardian decision
- Number of patients who continued into the double-blind phase
- Number and percentage of patients who were randomized
- Number and percentage of patients who were treated
- Number and percentage of patients who achieved dose level 3

- Number and percentage of patients who did not achieve dose level 3
- Reason for not achieving dose level 3
 - Hyperkalemia
 - Symptomatic hypotension
 - Renal dysfunction
 - Angioedema
 - Other adverse event
 - Unrelated to study treatment tolerability
- Number and percentage of patients who prematurely discontinued study treatment during the double-blind phase
 - Treatment unblinded by site (No, Yes)
- Number and percentage of patients who prematurely discontinued study treatment during the open-label phase
- Reason for premature discontinuation of study treatment (during double-blind phase and open-label phase, separately)
 - Adverse event
 - Death
 - Pregnancy
 - Study terminated by sponsor
 - Technical problems
 - Lost to follow-up
 - Physician decision
 - Subject/guardian decision
- Double-blind phase disposition
 - Completed
 - Death
 - Study terminated by sponsor
 - Physician decision
 - Subject/guardian decision
- Number and percentage of patients who continued into the open-label phase
- Open-label phase disposition
 - Completed

- Death
- Study terminated by sponsor
- Lost to follow-up
- Physician decision
- Subject/guardian decision
- Study duration in months [*(date of last contact/death – date of randomization +1)/30.3475*]

Additionally, listings of inclusion/exclusion criteria, screening/double-blind/open-label phase disposition, reason for withdrawal of consent and study treatment disposition will be provided.

